#### ADDITIONAL DOCUMENTS/ATTACHMENTS

01. 8/8/2016 [Data collection form](#) (r050607\_8-8-16\_CAREGIVER 90d data collection\_V8.docx)
02. 8/8/2016 [Other](#) (r050607\_8-8-16\_CAREGIVER 90d interview response options SHEET\_v2.docx)
03. 8/8/2016 [Email](#) (r050607\_8-8-16\_e-mail for post-study VSSP access\_v3.docx)
04. 8/8/2016 [Other](#) (r050607\_8-8-16\_Gift Card Mailing\_All groups\_adjusted WITH margin and logo\_v4.docx)
05. 8/8/2016 [Other](#) (r050607\_8-8-16\_mail 3\_All groups\_adjusted WITH margin and logo\_v1.docx)
06. 8/8/2016 [Consent Form](#) (r050607\_8-8-16\_MISTT Caregiver consent form\_FINAL\_level 9\_v2.docx)
07. 8/8/2016 [Consent Form](#) (r050607\_8-8-16\_MISTT Patient consent form\_FINAL\_level 9\_v2.docx)
08. 8/8/2016 [Consent Form](#) (r050607\_8-8-16\_MISTT verbal consent form for patient\_v4 FINAL\_v2.docx)
09. 8/8/2016 [Consent Form](#) (r050607\_8-8-16\_MISTT verbal phone consent for caregiver\_4 FINAL\_v2.docx)
10. 8/8/2016 [Data collection form](#) (r050607\_8-8-16\_PATIENT 90d data collection\_V12.docx)
11. 8/8/2016 [Other](#) (r050607\_8-8-16\_PATIENT 90d interview response options SHEET\_v1.docx)
12. 8/8/2016 [Other](#) (r050607\_8-8-16\_timelineINFOGRAPHIC DRAFT1.7 FINAL3 with 0.125 bleed.pdf)
13. 8/19/2016 [Consent Form](#) (r050607\_08-19-2016\_MISTT Patient consent form\_FINAL\_level 9\_v3.docx)
14. 8/19/2016 [Consent Form](#) (r050607\_08-19-2016\_MISTT Caregiver consent form\_FINAL\_level 9\_v3.docx)

**The Michigan Stroke Transitions Trial (MISTT): Improving Care
Transitions for Acute Stroke Patients Through a Patient-centered
Home Based Case Management Program**

NCT02653170

June 17, 2019

Analysis of Patient Outcomes

Among randomized participants, descriptive statistics of demographic and clinical data, including frequencies and contingency tables, were constructed for categorical data, while means and standard deviations were generated for continuous variables.

The original study protocol specified that the analytical model for the intention-to-treat (ITT) analysis of the primary study outcomes would involve testing the differences in the mean change over time (90-day minus 7-day values or “delta”) in each of the 3 treatment groups using a one-way ANOVA.¹ This approach is referred to as a “complete case analysis,” since for an individual participant to be included, it requires that data be available from both time points; if data are missing for either time point the participant is dropped from the analysis.

Subsequently, after completing data collection, we faced the problem of missing data at both the 7-day and 90-day time points, which negatively impacted the “complete case analysis” sample size. Specifically, only 180 patients had data available for the primary outcomes at both time points. To increase the number of observations available for the ITT analysis, we therefore modified the statistical model from the ITT “complete case analysis” to an ITT “available case analysis” which relied on the following linear regression model approach.²

The primary outcomes (PROMIS-10 GPH and GMH subscales, and PAM) were analyzed as linear (continuous) variables using Proc Mixed (SAS V9.4, Cary, NC); 7-day and 90-day outcomes were analyzed as correlated continuous responses within patient. The statistical model for the mean response comprised of an intercept, two indicators for group-2 and group-3 (group-1 as referent), one indicator for time 90-day (7-day as referent), and two group-by-time interactions. Hence the model for the mean response is:

$$\beta_0 + \beta_1 (\text{Grp2}) + \beta_2 (\text{Grp3}) + \beta_3 (90d) + \beta_4 (\text{Grp2} * 90d) + \beta_5 (\text{Grp3} * 90d).$$

The change from 7-day to 90-day in mean response in group-1 is β_3 ; the corresponding change in group-2 is $\beta_3 + \beta_4$. Hence, the group-by-time interaction coefficient β_4 is the comparison of group-2 to group 1; β_5 is the analogous comparison of group-3 to group-1. The combined 2-degree freedom test of the group-by-time interactions (i.e., $\beta_4=\beta_5=0$) identifies whether the mean change over time differed between treatment groups. We refer to this interaction as a difference-in-differences (D-in-D) analysis or result.² Pair-wise contrasts (with 95% confidence intervals) were generated to compare treatment groups with each other.

This “available case analysis” approach has the advantage of increasing the number of individuals that contribute to the ITT analysis, since participants with data available from only one of the 2 time points can still be included. Thus, while only 180 patients (with 360 observations, one for each time point) could be included in the complete case analysis, 214 patients (with 434 observations) were included in the available case analysis. The net effect of using the available case analysis approach is that it minimized the amount of missing data and thereby reduces its potentially negative impact on the primary results. However, it does not eliminate the problem of missing data, so there is still the need to use a multiple imputation procedure which we did as part of a subsequent sensitivity analysis.

Following completion of main effects models for all the primary outcomes, we tested whether adjusting for potential confounding variables resulted in a meaningful change in the results (defined as at least a 10% change in the beta coefficient representing the effect size of each treatment group). We developed the following list of a priori potential confounders: age, race, sex, time between admission and returning home, study site, stroke severity, discharge modified Rankin score (mRS), discharge destination (home, acute rehabilitation, sub-acute rehabilitation), and consented caregiver included (yes, no). We also adjusted the analysis for any variables that were not sufficiently balanced across the 3 treatment groups following randomization. After testing for confounding effects, we determined whether each of these same variables acted as a modifier of treatment effect by testing covariate*intervention interaction terms.

Secondary patient outcomes included depression symptoms (PHQ-9), Neuro-QOL anxiety, 90-day unplanned hospital readmissions, 90-day stroke/TIA recurrence, and 90-day home time. The PHQ-9 and Neuro-QOL anxiety outcome measures were analyzed using the linear regression model described above. The binary measures of 90-day readmissions, and stroke/TIA were analyzed using logistic regression. Ninety-day home time was analyzed using a 90-day-inflated negative binomial regression model (NBRM) due to the large number of patients with a home time of 90-days.

Sensitivity Analysis to Account for Missing Data

To assess the potential impact of missing data on primary patient outcomes, the analyses were repeated after missing data were generated using a multiple imputation procedure that generated 25 iterations of the fully imputed data. The linear regression results from the imputed data were then compared to the original analysis to determine if the presence of missing data had introduced any bias with respect to the statistical inferences drawn regarding overall treatment effect of the intervention (this approach can be regarded as a form of sensitivity analysis). To do this, we first applied the multiple imputation procedure 'Proc MI' (SAS software (SAS/ACCESS® 9.4) which is based on the missing at random (MAR) assumption where, using a Markov chain Monte Carlo (MCMC) method, missing outcome data are imputed using variables that are known or suspected to be associated with missing data. The Proc MI procedure imputed missing values for the primary outcomes (PROMIS-10 GPH, PROMIS-10 GMH, and PAM) each separately for the two different time points (7-day and 90-day), as well as the secondary outcomes of PHQ-9 and NeuroQOL anxiety. The imputation model included the treatment group (randomization arm) variable and the following 24 auxiliary variables: age, sex, race, stroke type (ischemic vs. hemorrhagic), past medical history/comorbidities (including history of stroke, TIA, myocardial infarction, coronary artery disease, atrial fibrillation, hypertension, hyperlipidemia, diabetes mellitus, depression, and heavy alcohol consumption), living alone prior to stroke event, having a consented caregiver, caregiver living with patient, relationship of caregiver to patient, severity of stroke (NIH Stroke Scale [NIHSS]/ Glasgow Coma Scale [GCS]), modified Rankin Scale (mRS) at discharge, score on 6-item cognitive screening test, study site, hospital discharge destination (home, acute rehabilitation, sub-acute rehabilitation), and the interval between admission and discharge to home (number of days). None of the auxiliary variables had any missing values. These auxiliary variables were chosen

on the basis that they were statistically significantly associated with missing outcomes data, or directly described the reason for missing-ness (i.e., health-related reason, refused, or no-contact). Trace plots (across 2,500 iterations) and autocorrelation plots were used to monitor the convergence behavior of the imputation algorithm. To allow for replication of the results, a random seed number was used for all the imputations. The final imputed data set contained 13,250 observations that resulted from 25 imputations of the original 265 cases. An identical MI approach was used to impute missing values for two of the secondary patient outcomes, including PHQ-9 and Neuro-QOL anxiety.

After generating the imputed data set, the same linear regression model used in the available case analysis (generated using SAS PROC MIXED) was applied to each imputed data set. The SAS PROC MIANALYZE procedure was used to summarize these results across the 25 imputed datasets, taking into account the uncertainty in imputation due to missing data. PROC MIANALYZE generates valid statistical inferences under a missing at random (MAR) assumption by combining the estimated model coefficients and associated covariance matrices across the multiple imputed datasets. As with the available case analysis, the quantities of substantive interest were the mean responses between the two time points and among the three study arms. In the full factorial model (main effects for the treatment groups and time, and their interactions), these quantities are the combined 2-degree freedom test of the group-by-time interactions (i.e., $\beta_4=\beta_5=0$), which identifies whether the mean change over time differed between treatment groups.

Because the MIANALYZE procedure is unable to generate parameter estimates and standard errors for interaction terms, the mean models were parameterized using parameters that directly represented the cell means for each of the 6 combinations of treatment group and time (i.e., Trt_group1= Usual Care at 7-day, Trt_group2= Usual Care at 90-day, Trt_group3= SWCM at 7-day, Trt_group4= SWCM at 90-day, Trt_group5= SWCM+MISTT website at 7-day and Trt_group6= SWCM+MISTT website at 90-day). From this parameterization, the group-by-time interaction effects in the mean responses were expressed as contrasts of the 6 cell means and evaluated using the TEST statement of PROC MIANALYZE with MULT option (a joint numerator 2-df test). The mean differences across the two time points for any two of the three study arms were compared using a t- distribution with df that take into account the uncertainty due to imputations.

Analysis for Caregiver Outcomes

Primary caregiver outcomes included the Bakas Caregiver Outcome Scale (BCOS) and PHQ-9 (depression), which were analyzed using the same linear regression model with group-by-time interactions as described above.

Secondary caregiver outcomes included PROMIS informational support, PROMIS emotional support, and unhealthy days. The support measures were also analyzed using the linear regression model, while the number of unhealthy days were analyzed using a zero inflated negative binomial model to account for the large number of caregivers who reported no unhealthy days.

We did not apply MI to caregiver outcomes as we lacked equivalent information on caregiver characteristics or details for why they did not participate, which could be used as auxiliary variables in the MI step.

REFERENCES

1. [name] MJ, [name] AK, Woodward AT, et al. Improving transitions in acute stroke patients discharged to home: the Michigan Stroke Transitions Trial (MISTT) protocol. *BMC Neurol* 2017;17:115.

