|       | 
Intervention-related Process data: Data relevant to the SW case management intervention will be collected by the SWs during the home visits and telephone follow-up calls. These data include the patient's bio-psycho-social assessment, details of the personalized case management treatment plan, progress toward goals, and details of any referrals made. These data elements are listed in Appendix 2c (Intervention-related process data). For those subjects who are given access to the MISTT Study website, data will be collected through Google Analytics concerning patient and caregiver use of the website. Data will include how often users log in, what pages they go to, how long they spend on those pages, the type of technology they use including type of browser, operating system, and use of mobile technology.
 
Outcome data: Outcomes data will be collected on all enrolled trial subjects (patients and caregivers) by telephone interviews conducted at 7-days and 90-days after the patient returns home. Patient related data elements are listed in Appendix 2d (Patient Outcomes), caregiver specific outcomes are listed in Appendix 2e (Caregiver Outcomes). The final choice of outcome measures will be decided upon by the research team after pilot testing of the candidate measures is completed. The following list includes the universe of candidate measures we are considering:
 
1) END Outcomes (Collected at 90-days): NIH PROMIS quality of life instruments including PROMIS Global QOL (Q10), and PROMIS self-efficacy (social interaction, medications, emotions and daily activities). NeuroQOL quality of life instruments including depression, anxiety, and satisfaction with social roles and activities, patient activation measure (PAM), hospital and ED visits since discharge, stroke recurrence, and 90-day home time (number of days at home during 90-day period).
 
2) Mediating Outcomes (Collected at 90-days): NIH PROMIS support measures including informational, instrumental, and emotional support. Dyad relationship scale, stroke knowledge test, stroke action test.
 
3) Effect modifier variables (collected at baseline, 7-days and/or 90-days): Demographics, stroke severity/stroke type, disability measures (mRS, Barthel Index (BI), ADL, IADL, cognitive function, social and living arrangements. CTM-15, technology use (Computer Self-efficacy, Attitudes to Technology, and Technology Utilization), medication adherence measures (Morisky scale), NeuroQOL quality of life instruments including communication, positive affect and well-being, emotional and behavioral dyscontrol.
 
4) Caregiver Specific Outcomes (collected at 7days and 90-days): Caregiver Strain index, Preparedness for Caregiving, mood, stroke knowledge, satisfaction, and function/disability (ADLs and IADLs). For enrolled patient-caregiver dyads we will also collect information from both parties on the Dyadic Relationship Scale, patient ADLs/IADLs, patient quality of life, patient depressive symptoms, and patient social support.
 
All baseline, process, and outcomes data will be entered into the Study's REDCap database. The management and protection of REDCap data is described in sections 22B and 22D.
 |                |

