| 22c. | 
Who will have access to the research data?
 
Only members of the research team will have access to the data. No identifiable data will be shared outside the research team.
  |
| 22d. | 
How will you ensure the confidentiality and/or anonymity of the research data? Include a description of the procedures and safeguards you will use, including if identifying information will be stored with the data.
 
Patient specific clinical data will be entered remotely by hospital study coordinators into a REDCap database using secure web-based data entry screens. Similarly, remote data entry in REDCap will also be used by the social workers (SW) to record data collected during home visits and telephone follow-up calls. Contact information required to find the patient's home be stored on secure password protected study laptop computers and cell phones – no hard copy forms that contain patient information will be maintain by the SWs. The outcomes data for this trial will be collected by phone by
   |

trained research assistants working under the supervision of the PI ([name]) and Project Manager ([name]). Data will be collected at two time points: 7 days and 90-days after returning home. Separate interviews will be conducted for patients and caregivers. The Project Manager, social workers, and research assistants conducting the telephone follow-up calls will all use secure (password protected) study-specific laptop and desktop computers. Laptop computer bags will be locked during transport and will be stored in locked offices. Desktop machines will be kept in a locked designated interview room in the Department of Epidemiology at MSU.

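### Readmission, stroke/TIA recurrence and home time appear to rest on a single 90-day phone interview and have no missing-data analysis, although the SAP records health-related reasons for missing outcomes

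*SAP*

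**What the plan says.** **Collection.** Protocol item 18 (Procedures, Outcome data) obtains outcomes "by telephone interviews conducted at 7-days and 90-days after the patient returns home". Its list of outcomes collected at 90 days includes "hospital and ED visits since discharge, stroke recurrence, and 90-day home time (number of days at home during 90-day period". Item 22d repeats the source: "The outcomes data for this trial will be collected by phone". Chart abstraction is described in item 18 for baseline clinical data only.

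**Analysis.** The SAP (Analysis of Patient Outcomes, secondary outcomes) says "The binary measures of 90-day readmissions, and stroke/TIA were analyzed using logistic regression". For home time it says "Ninety-day home time was analyzed using a 90-day-inflated negative binomial regression model (NBRM". It gives no denominator, no rule for a patient with no value, and no rule for deaths.

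**Missing data.** The SAP's sensitivity analysis imputes the three primary outcomes at both time points. It then adds: "An identical MI approach was used to impute missing values for two of the secondary patient outcomes, including PHQ-9 and Neuro-QOL anxiety". The other three secondary outcomes are not mentioned there. In explaining how the imputation variables were chosen, the SAP refers to some that "directly described the reason for missing-ness (i.e., health-related reason, refused, or no-contact".

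**The concern.** The available-case mixed model helps outcomes measured at both 7 and 90 days, because a patient with one value still contributes. An outcome measured once, at 90 days, gains nothing from it. A patient with no 90-day value adds nothing to the logistic or home-time likelihood.

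These are also the outcomes for which missingness is most likely to be informative. A patient who is in hospital, severely ill or dead at day 90 may have had the event and, for the same reason, have given no interview. The SAP accepts that missing data call for a sensitivity analysis of the symptom and quality-of-life scales, but provides none for these three outcomes. At stake is whether the reported event rates, and the differences between the three arms, describe the patients in the trial or only those well enough and willing to answer the phone.

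**Working it through.** **Inputs from the SAP:** 180 patients with primary outcomes at both time points; 214 patients and 434 observations in the available-case analysis; 265 cases; 25 imputations giving 13,250 rows.

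**The plan's own figures.** 25 × 265 × 2 time points = 13,250, which reproduces. The available-case figures do not:

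- 214 patients with at most two observations each give at most 2 × 214 = 428, fewer than 434.
- With 180 complete, 214 patients give 2 × 180 + 34 = 394 observations.
- With 180 complete, 434 observations need 180 + (434 − 360) = 254 patients.

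**How many lack 90-day data.** Taking 180 and 265 as correct, the upper limit applies if every single-time-point patient has only the 7-day value: 265 − 180 = 85. The lower limit applies if all of them have only the 90-day value: 265 − 214 = 51, or 265 − 254 = 11. So the range is 51–85 if the 214 is right and 11–85 if the 434 is right. These counts are for the primary outcomes and stand in for the event outcomes, whose counts are not given.

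**Worst-case bounds.** Let a share m be missing in each arm, with observed event rates p1 and p2. Each arm's full rate lies between (1 − m)p and (1 − m)p + m, so the risk difference lies within (1 − m)(p1 − p2) ± m.

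**Likely understatement (assumed rates).** The documents give no event rates. If the observed rate is p and missed patients have k times that rate, the observed-case rate is too low by m × p × (k − 1). The last column assumes p = 20% and k = 2 to 3.

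| Missing of 265 | m | Worst-case half-width of risk difference | Understatement of event rate |
|---|---|---|---|
| 11 | 4.2% | ±4.2 points | 0.8–1.7 points |
| 51 | 19.2% | ±19.2 points | 3.8–7.7 points |
| 85 | 32.1% | ±32.1 points | 6.4–12.8 points |

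With p from 10% to 30% and the same k, the understatement runs from 0.4 points (11 missing) to 19.2 points (85 missing).

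**Unequal missingness.** Suppose the observed rate is 20% in both arms, missed patients have 40% to 60%, and the arms differ by 10 points in the share missing. The full-cohort rates then differ by 0.10 × (0.40 − 0.20) = 2 points to 0.10 × (0.60 − 0.20) = 4 points, while the observed comparison shows none.

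**The case against.** The strongest reply is that the data source is inferred. Item 18 belongs to a pre-trial ethics application. It calls its list a set of candidates, to be settled after pilot testing, and the SAP's outcomes are worded differently (unplanned readmission, and TIA added to recurrence). The SAP does not say how they were ascertained, and the final 90-day instrument is not in the text available. This stands: phone collection is likely, not proven. Still, neither document names another follow-up source.

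Omission of patients without a value is the default behaviour of the named models, not a written rule. That also stands, but the plan states nothing to the contrary.

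Proxy respondents reduce some of the loss. Items 20h(1) and 24(b) provide them for patients who fail the cognitive screen or cannot complete it because of aphasia. They are not described as a remedy for a missed 90-day call.

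These are secondary outcomes, and the primary ones do have a missing-data analysis. This limits the weight of the point without closing the gap.

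**Conclusion.** The gap is real. Three event-type secondary outcomes, apparently collected once by phone, have no stated missing-data handling, although a plausible cause of missingness is tied to the events themselves. Understated event rates are likely, and bias in the arm comparison is possible in either direction. The extent runs from 4% to 32% of 265 patients and cannot be narrowed until 214 and 434 are reconciled. It rests on primary-outcome missingness as a stand-in, on 180 and 265 being correct and, for the bounds, on equal missingness by arm.

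Stronger readings are not supported:

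- A reader might infer that the trial's safety comparison fails. The SAP calls these secondary patient outcomes, and home time is partly a benefit measure. The study risks named in protocol item 21b are loss of confidentiality and increased stress, plus possible emergencies.
- A reader might infer that all 85 incomplete patients missed day 90. Some may have missed only the 7-day call.
- A reader might infer that the event always causes the missing value, or that downward bias is certain. A patient readmitted and then discharged can still be interviewed, and refusal and no contact are recorded reasons too, without counts.

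**What to change.** 1. Extend the missing-data sensitivity analysis to the three outcomes on all 265 cases. Use the auxiliary variables already held, which the SAP says are complete, and an imputation method suited to binary and count data; the MCMC method in the SAP is designed for continuous scales.
2. Show the readmission and recurrence contrasts with unknowns set to event and to no event, both overall and within the group missing for health-related reasons. This matters because imputation under missing at random does not address outcomes missing because of the event.
3. Report, by arm, the denominator for each outcome, the reasons for missingness and the known deaths. State how deaths enter home time and how the three outcomes were ascertained.
4. Reconcile 214 patients with 434 observations.

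The cost is SAP wording and some further analysis of data already held. The team should confirm that reasons are recorded by patient and time point, because no reason code appears among the 24 listed auxiliary variables. The downside is that the bounds may be wide.

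Two further steps are not proposed. A chart check of non-responders alone would make ascertainment depend on response status, and would need staff time and possibly new approvals. Counting a hospital stay as an unplanned readmission has no basis in the recorded reasons, none of which is a hospital stay.

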| 17.  | Project Description (Abstract)

Patients and caregivers often struggle to adjust to life after they leave the hospital following a stroke. Poor transitions in stroke patients can result in hospital readmissions, slow recovery, poor quality of life, dissatisfaction with care, and caregiver stress. Social workers play a vital role in healthcare by advocating for clients, providing counseling, and coordinating services. The Michigan Stroke Transitions Trial (MISTT) will implement a Social Work Case Management (SWCM) program, which through a combination of home visits and follow-up phone calls, will result in a personalized case management program designed to address unmet needs, increase patient engagement, decrease stress and improve quality of life. Access to accurate medical information during the transition period is also critical to patients and caregivers. The ideal information resource needs to be reliable, accessible, and responsive to the patient's changing needs. Therefore a second component to the MISTT study is the development of a study website that will serve as an information and support resource for patients and caregivers. The MISTT study will test the efficacy of these two complementary interventions in 480 acute stroke patients discharged from 4 Michigan hospitals. Patients will be randomly assigned to one of 3 groups: 1) usual care, 2) the SWCM program, or 3) the SWCM program plus the MISTT Study website. The intervention period will last 2 months and outcomes data (including quality of life) will be measured after 90-days.
   |  |   |   |                     |     |     |                                   |  |   |                                      |     |     |                                     |  |   |                                |     |     |  |                                       |   |                      |     |     |                                  |   |  |                                   |     |     |   |  |                                   |                                   |     |     |  |   |   |  |     |     |  |  |                                |  |  |     |  |

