| 20e.  | 
Provide the rationale for your sample size.
 
Sample size estimates were based on 2 outcome measures: Stroke-specific QOL (SS-QOL), and the Patient Activation Measure (PAM). Anticipated differences in the summary SS-QOL measure were obtained from a previous registry study of the PI ([name]) (Ref: Gargano et al, 2007) which found significant differences of 0.5 with a standard deviation of 1.9. Validation work on the PAM measure has shown that an average PAM score is 56 with a standard deviation of 13 (Ref: Hibbard et al, 2005), and that increases of 4.6 are clinically meaningful (Ref: Fowles et al, 2009). In all simulations, power was set to 80% with alpha= 0.05. All estimates were generated in SAS using the overall F test for a one-way ANOVA model based on the 3 group RCT design. To detect a 0.5 unit difference in mean SS-QOL scores with an assumed standard deviation of 1.9, a total sample size of 213 is required. To detect a 5 unit difference in mean PAM score with an assumed standard deviation of 13, a total sample size of 102 is required. When these baseline estimates were subjected to plausible changes in the effect size (through changes in detectable difference or the standard deviation) we obtained estimates between 63 or as high as 366. Our goal total sample size of 480 is therefore more than sufficient to detect clinically meaningful differences in these two outcomes.
 |  |

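### Home time cannot exceed 90 days, but the count part of its 90-inflated negative binomial, if fitted to home days as the SAP reads, has no upper limit and the wrong skew; days away from home is the better scale

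*SAP*

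**What the plan says.** The protocol (item 18, Procedures, end outcomes collected at 90 days) defines the outcome as "90-day home time (number of days at home during 90-day period"), so it is a whole number from 0 to 90.

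The SAP (Analysis of Patient Outcomes) gives it secondary status: "Secondary patient outcomes included depression symptoms (PHQ-9), Neuro-QOL anxiety, 90-day unplanned hospital readmissions, 90-day stroke/TIA recurrence, and 90-day home time". It then says: "Ninety-day home time was analyzed using a 90-day-inflated negative binomial regression model (NBRM"), and gives the reason: "due to the large number of patients with a home time of 90-days".

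For caregiver unhealthy days the same SAP (Analysis for Caregiver Outcomes) names a "zero inflated negative binomial model to account for the large number of caregivers who reported no unhealthy days".

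For home time the SAP mentions no reversal of the scale and no truncation at 90. It does not say whether treatment arm enters the inflation part, the count part or both, which coefficients are tested, or what effect is reported. It gives no proportion at 90, spread, effect size or number analysed.

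**The concern.** A 90-inflated negative binomial mixes a point mass at 90 with a negative binomial. The point mass absorbs the pile-up. Patients with fewer than 90 days are described by the negative binomial alone, which runs from 0 to infinity and is always right-skewed. Those patients' values stop at 89 and, with so many patients at the cap, can be expected to tail downwards.

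Fitted on that scale, the count part spends probability on impossible values. It also spreads its likelihood in the wrong direction, so it may separate the arms poorly when they differ in how long patients are away. At stake is the chance of detecting such a difference on one secondary outcome.

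Days away from home (90 minus home time) has its spike at 0 and its tail to the right, which is the shape a zero-inflated or hurdle negative binomial describes. The SAP already uses that kind of model for caregiver unhealthy days.

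**Working it through.** The plan has no power or fit figure for home time to reproduce. The check asks what the model does on the literal reading.

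**Inputs from the documents.** Range 0 to 90 (protocol item 18); three arms (item 17). The SAP states that "214 patients (with 434 observations) were included in the available case analysis" for the primary outcomes, so 214 / 3 ≈ 71 per arm. This is only approximate, because 214 patients at two time points can give at most 428 observations, and the number analysed for home time is not stated.

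**Assumed.** The share at 90, the mean days away among the rest, and a right-skewed distribution of days away capped at 90. Data were generated on the days-away scale, which favours the alternative model.

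**Model, literal reading.** P(Y = y) = π·1{y = 90} + (1 − π)·NB(y; μ, α), with
- NB skewness = (1 + 2αμ) / √(μ(1 + αμ)), always positive;
- impossible mass = (1 − π)·P(NB > 90).

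**Step 1: least-spread case.** As α goes to 0 the count part becomes Poisson. Its mass above 90 is under 1% at mean 70, 8% at 78, 12% at 80 and 27% at 85.

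**Step 2: fitted model, large samples.** With 50% at 90 and a mean of 15 days away, the fit is π = 0.49, μ = 75.0, α = 0.037.
- Skewness: αμ = 2.775, so (1 + 5.55) / √(75 × 3.775) = 6.55 / 16.83 = 0.39. The simulated values below 90 have skewness −1.86.
- Mass above 90: 0.174 of the count part; 0.51 × 0.174 ≈ 0.09 of the whole model.
- Mean: 0.49 × 90 + 0.51 × 75.0 = 82.4, equal to the simulated mean.

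Across 30%, 50% and 70% at 90 and mean days away of 8 to 35, values below 90 have skewness −0.9 to −2.0 against +0.1 to +1.6 for the fitted count part. The count part puts 17–20% above 90, which is 5–14% of the whole model. A zero-inflated negative binomial on days away puts 0–3.6% of the whole model beyond 90 days away.

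With 65% at 90 and a mean of 12 days away, about 16% of the count part lies above 90: 0.35 × 0.16 = 0.056 of the whole model.

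**Step 3: power at 71 per arm, two-sided 5%** (90-inflated model on home days against zero-inflated model on days away; rows 2 to 5 use 400 simulated trials each, Monte Carlo SE up to 2.5 points)

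| Share at 90 | Mean days away | Count part | Joint test |
|---|---|---|---|
| 65% in all arms | 12, doubled to 24 in one arm | 55% vs 78% | 43% vs 65% |
| 50% in all arms | 20 / 14 / 10 | 58% vs 81% | 43% vs 69% |
| 50% in all arms | 30 / 20 / 14 | 41% vs 81% | 30% vs 70% |
| 45 / 52 / 60% | 20 / 15 / 12 | 25% vs 48% | 49% vs 61% |
| 45 / 60 / 70% | 15 in all arms | no true difference | 69% vs 71% |

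In the last row the inflation-part test has 81% power under both models.

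**Step 4: size.** With no arm difference and 50% at 90, the literal model rejects in 0.8–2.5% (count part) and 2.5–2.8% (joint) of trials. The 65% setting gave about 2–3%. A repeat of the 65% setting (1,500 trials, three arms, likelihood-ratio tests, days away drawn as 1 plus a negative binomial with dispersion 1) gave 4.5% and 4.4%, with power 51% vs 73% (count part) and 37% vs 61% (joint). The power loss is therefore stable at about 22–24 points in that setting, while the degree of conservatism depends on the set-up.

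**The case against.** The strongest reply is that the SAP does not state the response scale. A model inflated at 90 can be fitted as a zero-inflated negative binomial on 90 minus home time and then described in terms of home days. On that reading the skew is right and most of the point disappears. This stands, so the point is conditional. The literal reading is still the natural one: home time is the named response, 90 is the named inflation point, and the authors used the term zero-inflated for another outcome.

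Several stronger inferences are tempting and not supported:
- **That the pile-up was ignored.** It was not; the inflation is there for it.
- **That the reported standard errors and test are wrong, or that a real effect was missed.** This would need the response scale and the data, and the documents give neither.
- **That the test produces false positives.** In every null setting simulated, the literal model's count-part and joint tests rejected at or below the nominal level.
- **That power is lost in general.** It is not lost when arms differ only in the share at 90.
- **That the negative binomial fails because its variance cannot fall below its mean.** In the 65% setting the values below 90 have variance 128 against mean 78, so this limit does not bite.
- **That two coefficients per arm is a fault peculiar to this model.** Any two-part model with arm in both parts has them, including the remedy.

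The remedy is not perfect either: it has no upper bound on days away and keeps a small impossible mass. The simulations also favour it by construction.

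**Conclusion.** The point holds conditionally. If the count part was fitted to home days without truncation, it has the wrong support whatever the data and, given the pile-up at 90, very probably the wrong skew. Under the assumed inputs, the cost when arms differ in days away is roughly 23 to 40 points of power on the count-part test and 12 to 40 points on the joint test, with tests that range from clearly conservative to close to nominal. The fitted mean is not distorted, and the comparison of shares at 90 is unaffected.

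The mismatch of support follows from the protocol's definition; every percentage rests on assumed rates. One secondary outcome is concerned, and the primary analysis is not. Changing it is worthwhile because the better model costs almost nothing.

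**What to change.** Replace the SAP sentence with one that:
- names the response as days away from home (90 minus home time);
- specifies a zero-inflated or hurdle negative binomial with treatment arm in both parts;
- tests the arm terms of both parts jointly (4 degrees of freedom for three arms);
- reports one marginal effect per comparison: the difference in mean home days with a bootstrap 95% confidence interval.

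If the model was already fitted to 90 minus home time, no rerun of the model is needed. Correct the sentence and state the direction of the reported ratio, since a ratio of days away and a ratio of home days point in opposite directions.

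A rank test alone is not a good substitute: Kruskal-Wallis had 14% power in the two settings with 50% at 90 where only days away differed.

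Cost: one sentence in the SAP and one rerun of a secondary model. The downside is a residual mass of 0–3.6%, in the settings examined, on more than 90 days away. A beta-binomial model, which respects the 0 to 90 limit, could be added as a sensitivity analysis if that matters.
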